substantial. In addition, massive bleeding after cardiac surgery is associated with higher rates of reoperation, morbidity, and mortality.³ Current practice per our institutional transfusion algorithm is to use fresh frozen plasma as first line therapy for factor mediated coagulopathy and bleeding after cardiopulmonary bypass.

Large prospective randomized studies directly comparing PCC to FFP in the setting of factor-mediated bleeding after cardiac surgery have not been conducted.

We hypothesize that PCC use will show a reduction in allogenic transfusion requirements in cardiac surgical patients with factor mediated postcardiopulmonary bypass bleeding.

2. Specific Aims:

Our aim is to conduct a prospective randomized controlled trial of patients undergoing elective cardiac surgery. We plan to preoperatively consent and enroll sufficient patients to reach a goal of 200 randomized patients (100 patients per arm) that demonstrate clinically significant microvascular bleeding and factor mediated coagulopathy after cardiopulmonary bypass. Randomized patients with clinically significant factor mediated bleeding will receive transfusion of PCC (Kcentra) (100 patients) or fresh frozen plasma (100 patients). Factor mediated coagulopathy will be defined per our current transfusion algorithm as PT >16.6 sec/ INR >1.6 sec. Primary outcome measures for efficacy will be total units of allogenic blood product transfused, and 24 hour postoperative blood loss. Outcome measure for safety will be rate of serious adverse outcomes. Analysis of coagulation factor levels will also be conducted prior to cardiopulmonary bypass, post cardiopulmonary bypass, and after product administration (PCC or FFP).

Hypothesis:

PCC arm will have same or decreased allogenic blood product transfusion rate and blood loss after cardiac surgery compared to patients receiving fresh frozen plasma.

3. Research Design and Methods:

A. Study Overview

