- 1) Mediastinal chest tube output must be ≤ 3 ml/kg/hr and 2 ml/kg/hr the first and second hour respectively, and 1 ml/kg/hr thereafter.
- 2) Hemodynamically stable.
- 3) Urine output ≥ 1 ml/kg/hr.
- 4) Normothermia ($>36^{\circ}\text{C}$)
- 5) Respiratory parameters fulfilled
 - pH ≥ 7.35 and ≤ 7.55
 - PaCO₂ ≥ 30 mmHg and ≤ 50 mmHg
 - PaO₂ ≥ 80 mmHg
 - SpO₂ $\geq 92\%$

Respiratory rate $\leq 25/\text{min}$

Discharge from the intensive care unit and hospital criteria

Current conventional discharge from the intensive care unit criteria and hospital will be used.

ICU discharge time will be recorded and traditionally assumes following criteria:

- Alert and cooperative
- No inotropic support
- No hemodynamically unstable dysrhythmia
- Adequate respiratory status
- Minimal chest tube drainage
- Urine output $\geq 0.5 \text{ ml/kg/hr}$

Discharge from the hospital will be recorded and traditionally assumes following criteria:

- Hemodynamically stable
- Stable cardiac rhythm
- Noninfected incisions
- Afebrile
- Ability to void and bowel movements
- Independent ambulation and feeding.

G. Data Collection

The following variables will be entered into a database:

1. Demographic:
 - a. Age
 - b. Sex
 - c. Society of Thoracic Surgeons (STS) risk score (where applicable)
2. Comorbidities:
 - a. History of cerebrovascular accident
 - b. History of vascular thromboembolic disease (arterial or venous thrombosis, organ ischemia secondary to thromboembolic phenomenon).
 - c. Coronary artery disease
 - d. History of atrial fibrillation
 - e. $\text{GFR} < 60 \text{ mL/min/1.73 m}^2$
3. Preoperative laboratory variables:
 - a. CBC, and the following if available preoperatively PT/ INR, APTT, Fibrinogen
4. Preoperative medications:
 - a. Anticoagulant medications
5. Intraoperative variables:
 - a. Procedure performed

- b. Initial or Redo-Sternotomy
 - c. Cardiopulmonary bypass time
 - d. Aortic cross clamp time (if applicable)?
 - e. Presence and (if present) duration of deep hypothermic circulatory arrest
 - f. Allogenic blood product utilization after cardiopulmonary bypass
 - g. Laboratory variables (CBC, PT/ INR, APTT, and Fibrinogen)
 - h. Anticoagulant (Heparin +/- other) and anti-fibrinolytic use (aminocaproic acid or tranexamic acid)
 - i. Direct transfusion related complications/reactions
 - 1. TRALI (Transfusion related acute lung injury) by standard definition¹⁶
 - 2. ABO/Non-ABO hemolytic reaction
 - 3. Anaphylactic or Allergic reaction

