6. Postoperative variables:
- a. Allogenic blood product transfusion
 - b. Mediastinal and chest tube output for 24 hours after chest closure
 - c. **Serious Adverse Events** occurring within 30 days of operation:
 - i. Thromboembolic events (new DVT or arterial thrombosis diagnosed by Doppler ultrasound, cerebrovascular accident or transient ischemic attack, new myocardial infarction, end organ ischemia secondary to thromboembolic phenomenon, all-cause mortality)
 - 1. The concern for thromboembolic complications is certainly present, and will be monitored closely as an adverse event in both treatment arms. The presence of clinically significant thromboembolic complications will be diagnosed as per current clinical practice in this patient population. It is assumed that clinical symptomatology or suspicion to such diagnoses will trigger diagnostic testing when deemed appropriate, and any confirmed diagnoses of thromboembolic complications will be noted. No specific screening tests will occur in patients enrolled for this study.
 - ii. Renal failure necessitating unplanned initiation of dialysis or hemofiltration
 - iii. Acute Respiratory Distress Syndrome (ARDS) by Berlin definition¹⁷
 - iv. Direct transfusion related complications/reactions
 - 1. TRALI (Transfusion related acute lung injury) by standard definition¹⁶
 - 2. ABO/Non-ABO hemolytic reaction
 - 3. Anaphylactic or Allergic reaction
 - d. Length of stay (ICU and total hospital stay)

H. Outcomes

All suspected outcome events will be evaluated in a standardized way by an adjudication panel that will be unaware of the patients' assignments.

In the study, outcome measures for efficacy will be total allogenic blood products transfused and 24 hour postoperative blood loss. Outcome measure for safety will be rate of serious adverse events.

Length of stay in the ICU and hospital will also be recorded in both groups.

I. Follow-Up

A telephonic assessment will be made by a study nurse at 30 days + 7 days. A standardized phone survey will be used to obtain information for assessing events of interest (Attached below).

J. Statistics/Power Analysis

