Limitations: If the study demonstrates lower transfusion requirements and blood loss in the PCC arm, further studies will need to address optimal dosing requirements. Current PCC dosing is based on INR and weight for patients on warfarin therapy. Should no difference be found between groups, or lower transfusion rate and/or postsurgical blood loss is found in the FFP arm, the question as to whether this represents a superior result of FFP or underdosing of the PCC arm will remain.

M. Anticipated Results

- a. PCC administration will reduce the amount of allogenic blood product transfused and amount of postoperative bleeding in patients undergoing cardiac surgery.
- b. Adverse event rate will be similar between the 2 treatment arms, representing the known risk associated with cardiovascular surgery.
- c. Perioperative transfusion related costs will be similar or lower in patients receiving PCC compared with FFP

N. Estimated Costs

Kcentra will be supplied and funded by CSL Behring (Melbourne, Australia). FFP if administered will be covered by the patient/payer as this treatment is the current practice standard. All laboratory testing not routine to this patient population will be funded by CSL Behring and is outline within the budget.

O. Research Materials

All data forms will be stored in individual patients study folders and handled securely for patient confidentiality. This data will be entered into an access database that is password protected.

P. Human Subjects

We will obtain informed consent from all participants prior to initiation of the study. Informed consent will meet the requirements of the code of federal regulations 21CFR 50.25 (elements of informed consent) and the IRB of this center. During informed consent for the study cardiac

surgical patients will be told that the chance of needing a transfusion in the perioperative period is around 11%. Should they meet criteria by our current transfusion algorithm to receive FFP, they would have been randomized to receive either FFP or the study PCC infusion. A copy of the consent form will be placed in the patient's medical records. The study will be stopped when 50 patients have received treatment in each study arm. Efficacy will be defined as either a statistically significant reduction in transfusion of allogenic blood products or 24 hour postoperative blood loss. Safety will be defined as similar rate of serious adverse outcomes in the PCC study drug arm to the standard therapy FFP arm.

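### Re-operation for bleeding or tamponade is not a collected variable, a listed serious adverse event or an outcome, so the efficacy and safety rules in 3.P can be met without counting it

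*Combined protocol and SAP*

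**What the plan says.** Section 1 (Background and Significance) gives, as an additional reason for the trial, that "massive bleeding after cardiac surgery is associated with higher rates of reoperation, morbidity, and mortality".

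Section 3.H has two efficacy measures: "outcome measures for efficacy will be total allogenic blood products transfused and 24 hour postoperative blood loss". For safety it says "Outcome measure for safety will be rate of serious adverse events". It adds length of stay, and a panel unaware of assignment adjudicates suspected outcome events.

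Section 3.G item 6 lists the postoperative data:
- transfusion, with no stated time limit;
- "Mediastinal and chest tube output for 24 hours after chest closure";
- serious adverse events within 30 days, in four groups (6.c);
- ICU and hospital stay.

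The first group in 6.c is thromboembolic and ends with "new myocardial infarction, end organ ischemia secondary to thromboembolic phenomenon, all-cause mortality". The second is "Renal failure necessitating unplanned initiation of dialysis or hemofiltration". The third is ARDS and the fourth is transfusion reactions.

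Section 3.P sets the success rules. On efficacy: "Efficacy will be defined as either a statistically significant reduction in transfusion of allogenic blood products or 24 hour postoperative blood loss". Safety is a similar serious adverse outcome rate in the two arms, with no margin given.

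**The concern.** The treatment is given to stop bleeding, yet the serious adverse event list has no event for failed haemostasis. It covers thrombotic, renal, lung and transfusion harms, and death. A return to theatre for bleeding or tamponade is a clinical failure that a reader would weigh against fewer units or less drainage, and Section 1 itself names it. Because 6.c reads as a closed list, following the plan as written leaves this event out of the safety comparison, and 3.P can reach both of its conclusions without it.

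At stake is the completeness of the benefit-harm comparison. The validity of the primary analyses is not in question.

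**Working it through.** **1. Where the event could have been recorded.**

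| Place | Content | Re-operation for bleeding or tamponade? |
|---|---|---|
| 3.G item 5 (intraoperative) | "Initial or Redo-Sternotomy" | No: this describes the index operation |
| 3.G items 6.a, 6.b, 6.d | Units, 24-hour drain output, stay | No |
| 3.G item 6.c | Four event groups, with all-cause mortality in the first | No |
| 3.H | Two efficacy measures, serious adverse event rate, stay | No |
| Telephone script, question 3 | Clots, heart attack, stroke, dialysis | No |
| Telephone script, questions 1 and 2 | Open questions on the time since discharge | Only by chance, and not for in-hospital events |

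The plan gives no general definition of seriousness that would bring the event into 6.c. The transfusion algorithms are figures missing from the text I had. Even if they mention a return to theatre, that would not make it a recorded variable.

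**2. Do the primary endpoints stand in for it?** Only partly. Blood loss is drain output for 24 hours from chest closure. Blood retained in tamponade does not reach the drain, and a return after 24 hours falls outside the window. Low recorded loss can therefore coexist with a re-operation. Extra units would count in the transfusion endpoint, but could not be attributed to a re-operation without the variable.

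**3. The plan's own figure.** Section 3.J claims more than 85% power for a 0.65 SD difference with 50 per group and a non-parametric test. Alpha is not stated, so I assume 0.05 two-sided.

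Power = Φ(0.65 × √(50 × ARE / 2) − 1.96), where ARE is the relative efficiency of the Wilcoxon test:
- ARE 1: Φ(3.25 − 1.96) = 90.2%
- ARE 0.955: Φ(3.18 − 1.96) = 88.8%
- ARE 0.864: Φ(3.02 − 1.96) = 85.6%

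The claim reproduces, and nothing here bears on the sample size.

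**4. Expected events.** The arm size is 50 treated (3.C, 3.E, 3.J, 3.P). Section 2 instead states 100 per arm, which is a separate inconsistency. The documents give no re-operation rate, so I assume 5-10%:
- 50 × 0.05 = 2.5
- 50 × 0.10 = 5

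**5. What a comparison could show.** For an illustrative split of 1/50 against 6/50 there are 7 events in 100 patients. The lower tail is [C(50,7) + 50 × C(50,6)] / C(100,7) = (99,884,400 + 794,535,000) / 16,007,560,800 = 0.0559. Doubling gives two-sided p = 0.112. With 2 events in one arm, the other would need 10 for p < 0.05 (p = 0.028); 9 gives p = 0.051.

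Two-sided Fisher power at 50 per arm, with assumed rates:

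| Rates | Power | N per arm for 80% (chi-square formula) |
|---|---|---|
| 5% v 10% | 6% | 435 |
| 5% v 15% | 24% | 141 |
| 5% v 20% | 51% | 76 |
| 10% v 20% | 20% | 199 |
| 10% v 30% | 64% | 62 |

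Approximate 95% CI half-width for the risk difference:
- 5% v 10%: 1.96 × √(0.05 × 0.95/50 + 0.10 × 0.90/50) = 10.3 points
- 10% v 20%: 1.96 × √(0.10 × 0.90/50 + 0.20 × 0.80/50) = 13.9 points

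The event can be described by arm, but not tested with useful power.

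**The case against.** The strongest reply is that the plan measures what its main rationale promises. The stated significance is fewer transfusions and fewer transfusion complications. Transfusion is a primary endpoint, transfusion reactions and ARDS are collected, and so is 30-day mortality. Reoperation is one of three harms in a single supporting sentence. All of this stands, so the omission should not be presented as the trial failing to measure its central harm.

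A reader might also infer that an excess of re-operations would go wholly unseen. The documents do not support that. Postoperative units, 24-hour drainage, stay and death would often move, and the open telephone questions could pick up later events. These are indirect signals, however, and none gives a count by arm.

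A reader might further take re-operation to be an endpoint protected from open-label bias. Section 3.D says otherwise: surgical and intensive care staff know the assignment, and re-exploration is a surgical judgement. Section 3.E adds that bleeding which continues without laboratory abnormality is usually surgical, so the event mixes surgical bleeding with product failure. Blinded adjudication can confirm that a re-operation took place and what was found. It cannot remove bias in the decision to go back.

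Finally, the operative record at this single centre would still hold the event, so the data could be retrieved later. That is true, but a count retrieved after the results are known is not prespecified, and the 3.P safety rule would still not have used it.

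**Conclusion.** The omission is real. Reoperation is named in Section 1 and is absent from 3.G, 6.c and 3.H, so both rules in 3.P can be met without counting it. The change is worth making, but no primary analysis, power statement or sample size becomes invalid without it.

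The size rests on assumed re-operation rates of 5-10%, giving 2.5-5 events per 50-patient arm. At those numbers the comparison is descriptive only, with a CI half-width of about 10 to 14 points in the scenarios shown.

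A reader might go further and conclude that PCC is likely to be declared safe while more patients return to theatre. Nothing in the documents suggests an excess in either arm. The point is only that the plan would not count one if it occurred.

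**What to change.** - **3.G item 6.c:** add *re-operation for bleeding or tamponade within 30 days of operation (date and time, surgical source found yes/no)*. Placing it in 6.c brings it into the 3.H safety outcome and the 3.P safety rule. Listing it only as a further postoperative variable would leave that rule unchanged.
- **Reporting:** also show it separately by arm as counts and a risk difference with an exact 95% CI, labelled descriptive, so that it is not lost in the overall event rate. This fits 3.J, which already treats serious adverse outcomes as exploratory.
- **Adjudication and monitoring:** send it to the existing blinded panel and add a row to the DSMB tables.

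**Cost:** one case report form item taken from the operative record for about 100 treated patients. No new visit or test is needed, and the sample size stays the same.

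**Downside:** one more outcome with few events, decided by an unblinded team. The surgical-source field helps readers interpret it but does not remove that limitation.

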Prothrombin complex concentrate use in hemophiliac patients dates back several decades, and has recently become the treatment of choice for management of bleeding in patients taking vitamin K antagonists (warfarin).⁷⁻⁹ Current formulations of inactivated PCC available in the United States include Bebulin (Baxter) which contains factors 2, 9, 10, and Kcentra (CSL Behring) which contains factors 2, 7, 9, 10. PCC administration in the perioperative setting including post-cardiopulmonary bypass coagulopathy and bleeding is common in European countries. Studies evaluating the efficacy of PCC's in this patient population have demonstrated faster normalization of INR, lower blood loss, and lower transfusion requirements.^{2,10,11} Historically, PCC use in the perioperative setting has been limited due to fear of thrombotic complications. Newer formulations of PCC's include a variety of anti-coagulants such as heparin, protein C & S, and anti-thrombin 3. Such additives are felt to reduce thrombotic risk when compared to PCC formulations void of these additives.¹² Thromboembolic events remain a concern when using any procoagulant including PCC's, especially formulations with activated factors such as FEIBA (Baxter), which contains activated factor 7. Inactivated PCC use has not been directly linked to significantly higher rates of adverse outcomes or thrombotic complications when compared to conventional therapies in surgical patients.^{2,10,13} Large prospective randomized trials comparing PCC and FFP in cardiac surgical patients to assess clinical outcomes and safety have not been performed. Distinct advantages to PCC administration compared with FFP include higher factor concentration despite significantly less infusate volume, ambient storage with rapid reconstitution, unnecessary blood group compatibility, lower risk of transfusion related complications such as acute lung injury and infection, along with potential cost savings.¹⁴ Current transfusion practices in European countries involve use of inactivated PCC in lieu of FFP.

The significance of this study is related to the potential for reduction in allogenic transfusion requirements and hence associated transfusion related complications. Transfusion reduction would also lead to institutional cost savings which in busy cardiac surgical practices could be

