The primary adverse event of concern in this study would be thromboembolic events. DSMB (anesthesiologist, hematologist, and statistician) will meet quarterly, and review all data from each study arm. Thromboembolic complications will be reviewed and clinical judgment will used to determine necessity of study termination. No formal stopping rules are feasible given the study size and low incidence of TEE.

Early termination of the study will ensue if adverse events in either study arm exceed acceptable level.

D. Randomization and Blinding

Upon consent for study participation enrolled patients will be randomized via computer-generated blocks and with stratification according to the surgical procedure to either receive PCC or FFP during cardiac surgery should they develop excessive microvascular bleeding in the

surgical field as determined by the surgical team in addition to a PT >16.6 sec/ INR >1.6 sec after cardiopulmonary bypass. The randomization assignments will be concealed in opaque envelopes and disclosed to the anesthesiologist caring for the patient. The surgical and intensive care personnel will not be blinded to the treatment arm, as transparency of transfusion product is necessary to prevent overdosage of PCC and potential thrombotic complications.

E. Interventions

Patients will be consented and enrolled in the study until 50 patients have received treatment in each arm of the study. Patients will be anticoagulated according to institutional practice with heparin 400 units/kg with goal ACT >400 prior to initiation of cardiopulmonary bypass. After cardiopulmonary bypass, patients will receive protamine at dose 0.01 mg/unit of heparin given with target ACT within 10% of baseline value. After protamine administration the ACT, CBC, PT/ INR, and fibrinogen, will be collected via preexisting arterial access. If ACT >10% baseline additional protamine will be given at the anesthesiologists discretion. Evaluation and determination of excessive microvascular bleeding in the surgical field will occur 10 minutes after return of ACT to within 10% of baseline. Patients with clinical evidence of excessive microvascular bleeding in the surgical field as determined by the surgical team, along with a PT >16.6 sec/ INR >1.6 sec will receive randomized treatment with either PCC or FFP.

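### Safety is judged only on a 'similar' pooled serious adverse event rate, so FFP-type reactions can partly offset a thromboembolic excess on PCC

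*Combined protocol and SAP*

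**What the plan says.** Section 3.H gives one measure for safety: "Outcome measure for safety will be rate of serious adverse events". Section 2 says the same in slightly different words. Section 3.J lists the rate as an exploratory endpoint and describes no analysis of its parts.

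Section 3.P gives the rule for the conclusion: "Safety will be defined as similar rate of serious adverse outcomes in the PCC study drug arm to the standard therapy FFP arm". It names no component, margin or confidence limit.

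Section 3.G, item 6.c, defines the list, which covers a 30-day window after surgery. Its four items are:
- (i) a thrombotic item, which begins "Thromboembolic events (new DVT or arterial thrombosis diagnosed by Doppler ultrasound, cerebrovascular accident or transient ischemic attack, new myocardial infarction" and also takes in ischemia of other organs from emboli and death from any cause;
- (ii) a renal item: "Renal failure necessitating unplanned initiation of dialysis or hemofiltration";
- (iii) ARDS by the Berlin definition;
- (iv) "Direct transfusion related complications/reactions", namely TRALI, hemolytic reactions and "Anaphylactic or Allergic reaction".

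The same transfusion reactions also appear in 3.G item 5.i as intraoperative variables, outside the serious adverse event heading.

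On direction, 3.C says "The primary adverse event of concern in this study would be thromboembolic events". Section 1 lists lung injury and allergic complications among the risks of FFP, and credits PCC with "lower risk of transfusion related complications such as acute lung injury and infection".

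**The concern.** A pooled rate is a reasonable summary when its parts are expected to move the same way. Here the protocol's own background links one part of the list to PCC and another to FFP. If PCC causes more thromboembolic events and FFP causes more transfusion reactions, the two differences have opposite signs and the pooled difference understates the first. Section 3.P then turns a small pooled difference into a statement that PCC is safe, although the event of main concern may differ.

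This is a matter of what is measured. A larger trial would estimate the same diluted difference more precisely, so the issue is separate from power.

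**Working it through.** **The plan's own figures.** The protocol gives no event rate, margin or power for safety. Its only power statement (3.J) concerns 24-hour blood loss: over 85% with 50 per group and a difference of 0.65 SD. With two-sided alpha 0.05 (assumed) and Wilcoxon efficiency 3/π, effective n = 50 × 3/π = 47.7, and power = Φ(0.65 × √(47.7/2) − 1.96) = Φ(1.216) = 88.8%. That figure reproduces but says nothing about safety.

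**Inputs.** All rates below are assumptions. Let t be the proportion with a thromboembolic event and r the proportion with a transfusion reaction, independent within a patient. Then pooled rate = 1 − (1 − t)(1 − r).

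**Thromboembolism 4% FFP vs 12% PCC, a true excess of 8 points:**

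| Reactions, FFP vs PCC | Pooled FFP | Pooled PCC | Pooled difference |
|---|---|---|---|
| 2% vs 1% | 1 − 0.96 × 0.98 = 5.9% | 1 − 0.88 × 0.99 = 12.9% | 7.0 points |
| 5% vs 2% | 1 − 0.96 × 0.95 = 8.8% | 1 − 0.88 × 0.98 = 13.8% | 5.0 points |
| 10% vs 2% | 1 − 0.96 × 0.90 = 13.6% | 1 − 0.88 × 0.98 = 13.8% | 0.2 points |

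Full offset needs (1 − r on FFP)/(1 − r on PCC) = 0.88/0.96 = 0.917. With 2% on PCC, that means 1 − 0.98 × 0.917 = 10.2% on FFP. The reaction excess must be about as large as the thrombotic excess.

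**A second set, adding other events at 10% in both arms.** Pooled rate = 1 − (1 − t)(1 − r)(0.90). With thromboembolism 5% vs 15%, the 10-point excess becomes:
- 8.1 points with reactions 2% vs 1% (16.2% vs 24.3%);
- 6.3 points with 5% vs 2% (18.8% vs 25.0%);
- 2.7 points with 10% vs 3% (23.1% vs 25.8%);
- 0.3 points with 12% vs 2% (24.8% vs 25.0%).

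With thromboembolism 5% vs 10% and reactions 10% vs 3%, the sign reverses: 1 − 0.95 × 0.90 × 0.90 = 23.1% on FFP against 1 − 0.90 × 0.97 × 0.90 = 21.4% on PCC.

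**What separation can deliver at 50 per arm.** Rates of 4% and 12% correspond to 2 and 6 events. Fisher's exact p = 0.27, and the power of that test at these rates is about 17%. Wilson 95% limits are 1.1% to 13.5% for 2/50 and 5.6% to 23.8% for 6/50. Newcombe's interval for the difference is:
- lower: 8.0 − √((12 − 5.6)² + (13.5 − 4)²) = −3.4 points;
- upper: 8.0 + √((23.8 − 12)² + (4 − 1.1)²) = +20.2 points.

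Even 2 vs 2 events would give about −9.9 to +9.9 points. For 5% vs 15%, 80% power needs 141 per arm.

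**The case against.** Several points on the other side have force.

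- **Thrombosis is already watched separately.** Under 3.C the DSMB reviews data by arm and looks at thromboembolic complications specifically. Item 6.c itemises the categories, and 3.H has a panel unaware of assignment evaluate outcome events. This protects patients during the trial and makes a later breakdown possible. But the DSMB review is by clinical judgment and serves the decision to terminate. It does not alter the measure in 3.H or the rule in 3.P.
- **A reader might infer that the two effects cancel.** The arithmetic supports offset, not general cancellation: with reactions of 2% vs 1%, 7.0 of the 8 points remain. PCC patients may also receive FFP, red cells, platelets and cryoprecipitate (3.E), which narrows the reaction contrast.
- **A reader might infer that the protocol expects more thrombosis on PCC.** It does not. Section 1 says inactivated PCC has not been directly linked to significantly higher rates, and 3.M anticipates similar adverse event rates. Thrombosis is a stated concern, which is reason enough to measure it cleanly.
- **A reader might infer that mild urticaria during FFP counts the same as a stroke.** The text does not establish this. Item 6.c is a postoperative list headed as serious, and intraoperative reactions are recorded under 5.i. What stands is an ambiguity: no seriousness criterion is given, and the 30-day window does not say whether 5.i events count.
- **A reader might infer that lung injury meeting both TRALI and ARDS is counted twice.** In a patient-level rate it is not.
- **Separation does not cure low power.** This stands. A threefold difference of 2 vs 6 events could still be called similar unless an interval is required.

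**Conclusion.** The point holds in a limited form. The safety conclusion rests on one pooled rate that mixes the adverse event of main concern with reactions the background ties to the comparator. Any FFP reaction excess therefore moves the result toward similarity.

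The size depends on rates the protocol does not give. For an assumed 8-point thromboembolic excess (4% vs 12%, independent components), the pooled difference ranges from 7.0 down to 0.2 points over the reaction rates tried. Near-complete masking requires a reaction excess close to the thrombotic one, so it is the extreme and not the expected case. The documents do not support saying that a thrombotic excess would vanish, only that it would be diluted by an amount that cannot be known in advance. The change is worth making because the remedy is cheap and the pooled rule does not answer the safety question that 3.C raises.

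**What to change.** - In 3.H, 3.J and 3.P, make the lead safety measure the proportion of treated patients with at least one adjudicated thromboembolic event.
- Take all-cause mortality out of item 6.c.i and report it separately. Otherwise a bleeding death would count as thromboembolic.
- Report direct transfusion reactions as a separate measure, and keep the pooled rate as descriptive.
- Give each as a between-arm difference with a 95% confidence interval. Base the safety statement on the thromboembolic interval and drop the word 'similar' as the criterion.
- State that 6.c.iv.3 counts only allergic reactions meeting seriousness criteria, and whether intraoperative reactions under 5.i enter the safety measure.

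**Cost.** Wording only, since every component is already collected. The downside is fewer events per category and wide intervals at 50 per arm (about −3 to +20 points for 2 vs 6 events). The report should say that the trial can describe thromboembolic risk but cannot establish similarity.
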